- Compare the diagnostic capability of two different methods of rhythm screening – time-limited patch ECG monitoring versus long-term wearable pulse wave monitoring through photoplethysmography – for AF detection and tolerability.

Influence on Clinical Care

- Compare the rate of initiation of anticoagulation and other AF-specific therapies at 12-months in the active monitoring cohort versus the matched observational control cohort.
- Compare the overall incremental costs of active monitoring for AF detection versus standard of care in the 3 years following the onset of monitoring.
- Identify the impact of active AF screening versus routine care on the time to first event of the following endpoints using claims data; A) among individuals diagnosed with new AF at 3 years following the initiation of screening, and B) the entire study cohort: utilizing claims data.
 - The combined endpoint of stroke/TIA, other systemic embolization, and/or myocardial infarction.
 - In the Medicare population only, in who mortality data will be available, the combined endpoint of stroke/TIA, other systemic embolization, myocardial infarction and/or death
 - The individual components of the combined endpoint.
 - All hospitalizations.
 - Hospitalizations for bleeding events.

4. Study Design

Participants

The study population will be derived from the Aetna Commercial Fully Insured and Medicare populations. From this population specific characteristics associated with an increased proportion of prevalent atrial fibrillation will be identified through claims data and utilized to identify a population at increased risk for undiagnosed atrial fibrillation.

Inclusion Criteria:

- Male or female age > 75 or
- Male age > 55, or female age > 65, and
- Prior CVA, or
- Heart failure, or
- Diagnosis of both diabetes and hypertension, or
- Mitral valve disease, or
- Left ventricular hypertrophy, or
- COPD requiring home O2, or
- Sleep apnea, or
- History of pulmonary embolism, or
- History of myocardial infarction, or
- Diagnosis of obesity

Exclusion Criteria:

- Current or prior diagnosis of atrial fibrillation, atrial flutter or atrial tachycardia
- Receiving chronic anticoagulation therapy
- Hospice care
- End stage renal disease
- Diagnosis of moderate or greater dementia
- Implantable pacemaker and/or defibrillator
- History of skin allergies to adhesive patches
- Known metastatic cancer

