- Aetna Compassionate Care Program (ACCP) participants – individuals with advanced illness and limited life expectancy

Through the use of the above inclusion and exclusion criteria, but not excluding patients with a diagnosis of atrial fibrillation or flutter, we expect to identify a population with an overall prevalence of known AF of 10-15%. Based on prior studies supporting that 30% of the total AF population is undiagnosed, then the total AF population (X) = diagnosed AF population (0.7X) + undiagnosed AF population (0.3X). Therefore with a 12% prevalence of diagnosed AF representing only 70% of the total AF population that would suggest that the true total AF population prevalence is 17%, and therefore the prevalence of undiagnosed AF would be ~5%.

[figure not shown]
Participant Recruitment

Eligible Aetna members will be contacted by letter, electronically or paper, (Appendix 1) with information about the study and an invitation to learn more via a study-specific web site as well as the option to discuss with a research coordinator. Once an individual agrees to participate they will be directed to an online Informed Consent Document, or if they prefer, one will be mailed to them.

A conservative estimate is that 5% of the approached population will agree to participate in the study. With an estimated >100,000 eligible participants to approach this should allow for the recruitment of a total of 2000 individuals for randomization and allow for development of a matched observational cohort of 4000 individuals.

It is anticipated that 10,000 invitations will be sent out to eligible Aetna members on a rolling basis every one to two weeks with invitations continuing until ~2250 (to account for an assumed 12% drop-out in first year) individuals have agreed to participate and signed the informed consent.

Study Flow

Randomized Cohort

Following informed consent individuals will be randomized to either the immediate screening arm or the delayed screening arm. All individuals randomized to immediate screening will be sent their monitoring device(s) immediately after signing their informed consent. Their 4 months of monitoring will begin the first day their monitoring device is activated. Those randomized to delayed monitoring will receive their monitoring device(s) 4 months after the date of their informed consent being signed, with their 4 months of monitoring also starting the first day their monitoring device is activated.

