During the 4-month monitoring period all individuals will undergo continuous single-lead ECG monitoring with a wearable patch (iRhythm ZIO® XT Patch) during the first and last 2 weeks of the 4-month study period (total of 4 weeks).

Consenting participants will also be invited to participate in a ~500 person sub-study to wear an additional monitoring device; a wristband photoplethysmography-based device (Amiigo). Enrollment in this sub-study will be limited to individuals who already own and use a smartphone (iOS or Android). Volunteers will be asked to sign a second informed consent to participate in this sub-study.

Monitoring Devices

All individuals randomized to active screening will receive a ZIO XT Patch (<http://www.irhythmtech.com/zio-solution/zio-patch/>). The ZIO XT Patch will be mailed to the participant's home with instructions how to place and activate the patch. A link to an instructional video will also be provided as well a call-in number for support.

They will be asked to wear it for the first 2 weeks, and again during the final 2 weeks of the 4-month monitoring period. While wearing the patches a single-lead ECG is recorded

continuously. After the 2-week monitoring period the patch is mailed back to iRhythm in a pre-prepared package where the rhythm is analyzed.

A second exploratory method of rhythm detection in a self-identified subset of the same patients will be carried out using a wristband developed by Amiigo (<https://amiigo.com/>) that will allow for long term, non-obtrusive monitoring on a daily basis throughout the 4 month period. The Amiigo determines resting pulse rate using photoplethysmography; a technique

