4 month assumptions: 5% incidence AF in monitored, 0.5% in non-monitored.

[figure not shown]
	Sample Size Active Monitoring	Sample Size Delayed Monitoring	Event Rate Active Monitoring	Event Rate Delayed Monitoring	Power
As Designed	1000	1000	5%	0.5%	>0.99
Minimal Size	320	320	5%	0.5%	0.90
Minimal Size, Increased Event Rate	430	430	5%	1.0%	0.90

12 months assumptions: 7% incidence AF in monitored, 2% in the observational control arm.

	Sample Size Active Monitoring	Sample Size Matched Observational Cohort	Event Rate Active Monitoring	Event Rate Delayed Monitoring	Power
As Designed	2000	4000	7%	2%	>0.99
Minimal Size	400	400	7%	2%	0.90
Minimal Size, Increased Event Rate	1278	1278	7%	4%	0.90

3-year assumptions:

- 10% prevalence of AF in both monitored and observational control arms.
- A 7.5% event rate in observation cohort (based on ACTIVE A data) and a 50% reduction in the monitored cohort due to earlier diagnosis prior to having an event or symptom.

Power = 0.81 for log rank test with assumptions as below (rates are cumulative):

	Actively Monitored		Control	
Sample size with AF (10% prevalence in both groups)	n=200		n=400	
	Diagnosis Rate	Event Rate	Diagnosis Rate	Event Rate
6 months	5%	1%	0.5%	4%
15 months	7%	2%	3%	9%
36 months	10%	5%	10%	12%

A separate, detailed statistical analysis plan will be developed.

8. Possible Benefits

It is possible that participants could benefit by receiving a diagnosis of AF before they would otherwise, which could possibly lead to changes in therapy that might decrease their risk of thromboembolic events.

As determining the optimal method for population screening for AF is recognized as being an important unmet need, the results of this study could benefit a substantial proportion of the population through helping identify and refine screening methods. In addition, participation in this study will provide a greater understanding of the characteristics (e.g. frequency, duration, rate, time of day) of arrhythmias episodes that are or are not associated with symptoms.

9. Possible Risks and Analysis of Risk/Benefit Ratio

There is minimal risk to a patient receiving cardiac rhythm monitoring and, in general, complications are related to the adhesive that affixes the ZIO XT Patch to the subject. The FDA has cleared the ZIO XT Patch for use for patients who do not have known skin allergies or a family history of skin allergies. Company experience for skin allergies in 2011 is 0.02% in over 30,000 patients.

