Upon signing the informed consent document, subjects will be randomized to either the immediate monitoring group or delayed monitoring group by random number generator. The random number generator uses Ruby's pseudo-random number generator functionality (PRNG) implemented as a modified Mersenne Twister with a period of 2**19937-1. The subject's group assignment will be sent to the STSI coordinating team. Continued eligibility of all randomized subjects for the study will be confirmed upon enrollment using Aetna databases for all inclusion and exclusion criteria.

For subjects randomized to the immediate monitoring group, the first Zio patch will be sent upon confirmation of continued eligibility. The first Zio patch will be worn by subjects in the immediate monitoring group during the first two weeks of the 4-month monitoring period. A second Zio patch will be sent to subjects in the immediate monitoring group for wear during the final two weeks of the 4-month monitoring period.

A subject will be considered withdrawn from the study if they inform the STSI study coordinating center that they wish to withdraw or if they have not initiated use of the first Zio patch after 3 notifications (e-mail/phone/e-mail) from the coordinating center.

Intention-to-treat analysis for the RCT will include all participants who are enrolled in the study according to their randomly assigned group (immediate monitoring or delayed monitoring) with the RCT follow-up time for subjects in the immediate monitoring group beginning at date of enrollment and ending at 4 months following date of enrollment or the time of completion of monitoring with their final patch, whichever is longest, and for subjects in the delayed monitoring group beginning at date of enrollment and ending at 4 months following the date of enrollment.

The per protocol analysis of the RCT will include immediate monitoring participants had analyzable data from the Zio patch for at least 30 continuous minutes any time during their assigned monitoring period and all participants in the delayed monitoring group who did not withdraw from the study prior to 4 months of follow-up.

Delayed Monitoring Group

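### The skin-allergy exclusion is narrower than the device clearance the protocol cites, and the only eligibility check described names no source that would show it

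*Protocol*

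**What the plan says.** **Who is excluded.** The exclusion lists in Protocol Section 4 and SAP Section 4 use the same words: "History of skin allergies to adhesive patches". Neither mentions other skin allergies or family history.

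**Who the device is for.** Protocol Section 9 names the adhesive as the general source of complications. It then says that the FDA "cleared the ZIO XT Patch for use for patients who do not have known skin allergies or a family history of skin allergies", and gives a company rate for skin allergies of 0.02% in more than 30,000 patients.

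**How eligibility is checked.** Under SAP Section 4, randomisation comes first: "Upon signing the informed consent document, subjects will be randomized to either the immediate monitoring group or delayed monitoring group". Then: "Continued eligibility of all randomized subjects for the study will be confirmed upon enrollment using Aetna databases for all inclusion and exclusion criteria".

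**When and how the patch is sent.** Protocol Section 4 (Study Flow) states: "All individuals randomized to immediate screening will be sent their monitoring device(s) immediately after signing their informed consent". The SAP says that for the immediate group "the first Zio patch will be sent upon confirmation of continued eligibility". Delivery is by post: "The ZIO XT Patch will be mailed to the participant's home with instructions how to place and activate the patch".

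**The concern.** The protocol states the population for which the device is cleared, then sets an entry rule that admits a wider one and does not comment on the difference. Adhesive reactions are the main complication it names. Each participant is planned for four weeks of patch wear, and a wristband participant flagged for possible AF while not wearing a patch is sent one more for two weeks.

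The plan describes no later step that would catch the mismatch. Patches are self-applied at home, and the one described check relies on insurer data. If the wider entry is deliberate, the documents do not say so. If it is not, people can be sent a device outside the clearance that the protocol itself uses to support a minimal-risk statement.

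**Working it through.** No design figure depends on this point, so the main check is a comparison of the texts. The arithmetic only gives scale.

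**1. Clearance against exclusion.**

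| Person | Within the clearance as stated in Protocol Section 9? | Excluded by Section 4 of either document? |
|---|---|---|
| Known allergy to adhesive patches | No | Yes |
| Another known skin allergy | No, on the plain reading | No |
| Family history of skin allergy only | No | No |

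The second row depends on how broadly Section 9 is read. The third does not.

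**2. Can the described check see the criterion?** SAP Section 2 lists membership, medical case, claims, episode groups, care management, the health profile database, pharmacy data and the study enrolment database. The enrolment database is described by content: enrolment and group, patch dates and serial numbers, withdrawals, adverse events, sub-study participation and communications. No listed source names an adhesive-allergy or family-history item. Protocol Section 17 adds a general review of eligibility and source data, but against the protocol's own criteria, so it inherits the narrower wording.

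**3. Order of steps, immediate arm.**
- Protocol: consent, randomisation, device sent immediately.
- SAP: consent, randomisation, database confirmation, device sent.

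Under the protocol's order the database check need not precede mailing. The delayed arm is not affected: its first patch goes out 4 months later, after the check at enrolment.

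**4. Scale at the cited rate.** Inputs: 0.02% and 30,000 (Protocol Section 9); 2,000 randomised as designed (both documents); about 2,100 to be consented (SAP Section 4); about 2,250 to be consented (Protocol Section 4).

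- Cases behind the rate: 0.0002 × 30,000 = 6.
- Expected cases = n × 0.0002. Chance of at least one = 1 − (1 − 0.0002)^n.

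| n | Expected cases | Chance of at least one |
|---|---|---|
| 2,000 | 0.40 | 33% |
| 2,100 | 0.42 | 34% |
| 2,250 | 0.45 | 36% |

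The documents do not say how many participants fall outside the clearance. As an assumption only, 1% to 20% of 2,000 to 2,250 would be 20 to 450 people. They give no reaction rate for such people, so no excess can be calculated.

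**5. Does it touch the primary analysis?** The plan states power above 0.99 for 5% against 0.5% with 1,000 per arm. The normal approximation for two proportions (two-sided alpha 0.05) gives:

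- Null SE = √(2 × 0.0275 × 0.9725 / 1,000) = 0.00731; alternative SE = √((0.05 × 0.95 + 0.005 × 0.995) / 1,000) = 0.00724.
- z = (0.045 − 1.96 × 0.00731) / 0.00724 ≈ 4.23, so power is above 0.999, which agrees with the plan.
- With 20% fewer per arm (800, a deliberately large assumed loss), power is 0.9998.

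**The case against.** **Section 9 is a risk narrative and sets no eligibility rule.** Its context is the adhesive, and the 0.02% figure plainly concerns reactions to the patch. Known skin allergies could therefore be shorthand for the adhesive allergy that Section 4 excludes. This is a fair reading, and it weakens any claim of outright contradiction. It does not cover family history, which Section 9 names and neither exclusion list mentions.

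**A reader might infer that allergy is checked only in insurer databases.** The documents do not establish this. The SAP sentence concerns continued eligibility and does not rule out other checks. Participants also pass through a website, a consent document and an optional talk with a coordinator. The consent form and the Appendix 1 text are not in the copy reviewed, and a self-report question could sit there. What stands is that the database confirmation is the only specific check described.

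**A reader might infer that the exclusion removes almost nobody.** This is also unsupported. Claims carry diagnosis codes, the health profile database covers more than 84 conditions that are not listed, and care management holds survey and assessment data. Some of these could record an allergy, although none is said to.

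**Reactions are already recorded.** Adverse events are logged with type and date, and early discontinuation with its cause is a safety endpoint. That is correct, but it documents reactions after the patch has been worn and does not settle who should be sent one.

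**Conclusion.** The point holds as a minor participant-protection and consistency issue. The stated clearance and the exclusion do not describe the same population: certainly for family history, and on the plain reading for other skin allergies too. The one specific check described comes after randomisation and names no source for the criterion, and the two documents order mailing and checking differently in the immediate arm.

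The expected size is small: 0.40 to 0.45 reactions among 2,000 to 2,250 participants. This assumes that the cited 0.02% applies. It may not apply outside the clearance, and the documents give no other rate.

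Two further inferences are tempting and should not be drawn. One is that reactions would noticeably lower AF detection: power stays above 0.999 even after an assumed 20% loss per arm. The other is that the observational comparison is compromised because controls cannot be screened for allergy. Controls receive no patch, and nothing in the documents links this criterion to an imbalance in outcome.

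**What to change.** 1. Reconcile the exclusion in Protocol Section 4 and SAP Section 4 with the clearance statement in Protocol Section 9, so that all three describe one population. Which wording is right is for the sponsor and investigator to decide. If the wider entry is intended, say so and give the reason.
2. Add a self-report item for this criterion to online enrolment, before randomisation and in addition to the database confirmation. If the consent or enrolment pages already contain one, cite it in both documents. Asking before randomisation avoids removing people after they have been assigned to an arm.
3. Reconcile the mailing rules in Protocol Section 4 (Study Flow) and SAP Section 4, so that no patch is mailed before eligibility is confirmed.

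The cost is aligned wording and one question on an existing enrolment page. The downside is that some volunteers will be screened out before randomisation; the documents do not allow that number to be estimated. Sample size and analysis need no change.

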become more ubiquitous in wearable mHealth devices. Data is analyzed on a near-continuous basis for rhythm abnormalities as well as other physiologic parameters. Individuals agreeing to be monitored with the Amiigo will have one sent to them along with a charging device and instructions to download the smartphone app. Only routine fitness data, such as activity, calories burned and sleep duration will be available to Amiigo users via the app. Individuals will be encouraged to wear the device as frequently as possible, night and day, throughout the 4-month monitoring period. Rhythm monitoring will occur passively while a subset will also be prompted daily to sit quietly for 60 seconds to allow for active monitoring. As the Amiigo's rhythm detection capability is exploratory anyone identified to potentially have AF during a period when they are not concurrently wearing a ZIO XT Patch, will be sent another ZIO XT Patch to wear for an additional 2 weeks in order to confirm the diagnosis of AF.

Observational Control Group

A risk-matched observational cohort will be developed from among individuals deemed eligible for study participation but not having the opportunity to participate in the randomized study (i.e. randomized cohort filled prior to their being invited). Individuals will be matched 2:1 with the 2,000 actively monitored cohort based on age, gender, CHA₂DS₂-VASc score, and Propensity Score. An individual's CHA₂DS₂-VASc score can range from 0 to 10 and is based on the composite value of points determined by the presence of cardiac failure or dysfunction (1 point), Hypertension (1 point), Age \geq 75 (2 points), Diabetes (1 point), Stroke (2 points)-Vascular disease (1 point), Age 65–74 (1 point) and Sex category (1 point for female).

The observational period of controls will begin the day their matched actively monitored counterpart signed their informed consent.

Atrial Fibrillation Diagnosis

In the actively monitored cohort a diagnosis of atrial fibrillation/flutter will be made based on documented evidence of a minimum of 30 seconds of continuous atrial fibrillation or flutter confirmed by ECG monitoring with the ZIO XT Patch during the active monitoring period, or the new clinical diagnosis of atrial fibrillation or flutter based on claims data. For the control cohort a new diagnosis will be based solely on a new clinical diagnosis documented in claims data.

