- b. In the sub-population of individuals newly diagnosed with AF during the 3-year follow-up.

9. Compare time to first event of the combined endpoint of stroke, systemic embolism, myocardial infarction or death among subjects in the Medicare population at baseline in the actively monitored cohort with the matched observational control cohort at 3 years:

- a. In the entire cohorts.
- b. In the sub-population of individuals newly diagnosed with AF during the 3-year follow-up.

10. Compare time to first event of individual components of the combined endpoint (stroke, systemic embolism, myocardial infarction) in the actively monitored cohort with the matched observational control cohort at 3 years:

- a. In the entire cohorts.
- b. In the sub-population of individuals newly diagnosed with AF during the 3-year follow-up.

11. Compare time to first event of all-cause hospitalizations in the actively monitored cohort with the matched observational control cohort at 3 years:

- a. In the entire cohorts.
- b. In the sub-population of individuals newly diagnosed with AF during the 3-year follow-up.

12. Compare total number of all-cause hospitalizations in the actively monitored cohort with the matched observational control cohort at 3 years:

- a. In the entire cohorts.
- b. In the sub-population of individuals newly diagnosed with AF during the 3-year follow-up.

Analysis of Safety Endpoints

1. Compare time to first event of hospitalization for a primary bleeding diagnosis in the actively monitored cohort with the matched observational control cohort at 3 years:
 - a. In the entire cohorts.
 - b. In the sub-population of individuals newly diagnosed with AF during the 3-year follow-up.
2. Compare incidence of the detection of non-AF, but other actionable heart rhythm issues during monitoring in the actively monitored cohort with the matched observational control cohort in the entire cohorts at 3 years.
3. Describe incidence, timing and etiology of discontinuation of active monitoring in the monitored cohort.

Exploratory Analysis

1. Evaluate the correlation between AF detected by the Amiigo wristband with the incidence of AF detected by the Zio patch in active monitoring cohort during 4 months of active monitoring.

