5. ENDPOINTS AND COVARIATES

[Data source in brackets]

Primary Endpoint

1. Atrial Fibrillation/Flutter: new diagnosis of atrial fibrillation or atrial flutter defined as:
 - a. ≥ 30 seconds of atrial fibrillation or flutter diagnosed and adjudicated on the iRhythm output (monitored cohort) [PI Diagnosis Database]
 - i. Date
 - ii. Duration
 - b. Claim for atrial fibrillation/atrial flutter with ICD-9 code 427.1 or 427.2 or ICD-10 code I48.91 or I48.9 [Aetna Claims Data; Aetna Medical Case]
 - i. Date

Secondary Endpoints

1. Atrial Fibrillation/Flutter: HPD algorithm [Aetna HPD Database]
2. Anticoagulation: Drug NDC codes for new refill for any:
 - a. Anticoagulant (dabigatran, rivaroxaban, apixaban) or
 - i. Date
 - b. P2Y12 Antagonists (clopidogrel, prasugrel or ticagrelor) without a new diagnosis of acute coronary syndrome
 - i. Date
4. Other AF-related therapies (i.e. antiarrhythmic agents excluding beta-blockers and calcium channel blockers, cardioversions, ablation procedures or hospitalizations with a primary diagnosis of AF)
5. UtilizationCommented [[name]]: Need to further define
3. Stroke-related visits during follow-up [Aetna Medical Case]
 - a. Inpatient
 - b. ER
 - c. Time to first stroke-related event (Inpatient or ER)
4. Myocardial infarction-related visits during follow-up [Aetna Medical Case]
 - a. Inpatient
 - b. ER
 - c. Time to first myocardial infarction-related event (Inpatient or ER)
5. Systemic thromboembolism-related visits during follow-up [Aetna Medical Case]
 - a. Inpatient
 - b. ER
 - c. Time to first systemic thromboembolism-related event (Inpatient or ER)
6. Death (Medicare population): [Aetna ATV; Aetna Membership Table]
 - a. Time to death (within 1 month of date)

- b. Cause of death
- 7. All-Cause Hospital Admissions [Aetna Medical Case]
 - a. Total number
 - b. Total length of stay
 - c. Individual admissions
 - i. Primary diagnosis
 - ii. Date
 - iii. Length of stay

Safety Endpoints

- 1. Hospital admission for primary bleeding diagnosis: [Aetna]
- 2. Incidence of non-AF, but other actionable heart rhythms captured by device (and confirmed by PI) [PI Diagnostic Database]
 - a. Atrial Tachycardia with variable block of > 30 seconds
 - b. Ventricular Tachycardia >5 beats
 - c. Pauses \geq 5 seconds
 - d. AV block
- 3. Early discontinuation of active monitoring in monitored cohort [Scripps Study Database]
 - a. Date of discontinuation
 - b. Cause of discontinuation

Exploratory Endpoint (Amiigo)

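### AF found on wristband-triggered extra patches counts toward the primary endpoint without being separated, so the reported yield mixes two screening strategies and the device comparison leans toward association

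*Protocol*

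**What the plan says.** **Scheduled screen.** Protocol Section 4 (Study Flow) has all monitored participants wear the patch "during the first and last 2 weeks of the 4-month study period (total of 4 weeks". SAP Section 4 likewise describes a first and a second patch.

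**Wristband sub-study.** The same Protocol section states: "Consenting participants will also be invited to participate in a ~500 person sub-study to wear an additional monitoring device". Participants are self-identified smartphone owners, and the split by arm is not given. If the wristband suggests AF while no patch is being worn, the person "will be sent another ZIO XT Patch to wear for an additional 2 weeks in order to confirm the diagnosis of AF". Protocol Section 5 makes clear that this extra patch is worn together with the wristband.

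**What counts as AF.** For the monitored cohort, Protocol Section 4 (Atrial Fibrillation Diagnosis) requires "documented evidence of a minimum of 30 seconds of continuous atrial fibrillation or flutter confirmed by ECG monitoring with the ZIO XT Patch" within the active monitoring period, or a new diagnosis in claims. The device part of the primary endpoint in SAP Section 5 is at least 30 "seconds of atrial fibrillation or flutter diagnosed and adjudicated on the iRhythm output (monitored cohort"). Neither definition refers to the type of patch.

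**Window.** In SAP Section 4 the immediate arm is followed to 4 months or "the time of completion of monitoring with their final patch, whichever is longest". The delayed arm stops at 4 months, which is when its devices are sent.

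**Device comparison.** SAP Section 3 plans to "Evaluate the correlation between AF detected by the Amiigo wristband with the incidence of AF detected by the Zio patch" over the 4 months of active monitoring, with no restriction to shared wear. The exploratory endpoint in SAP Section 5 does restrict true and false positives to overlapping monitoring.

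**Data held.** SAP Section 2 records patch serial numbers, activation dates and sub-study participation. No planned analysis uses them to tell scheduled from triggered patches.

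**The concern.** A triggered patch exists only because a device not yet validated for rhythm detection raised an alarm, and only in people who volunteered for that device. Its AF findings enter the primary count unmarked. A reader of the results could not tell how much of the yield came from the two scheduled patches offered to everyone and how much from wristband-prompted ECG in a subset. That matters to anyone who wants to apply the two-patch schedule elsewhere. The same cases carry into the 12-month comparison and the 3-year AF sub-population.

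The device comparison has a related problem. The chance of a positive patch depends on how long a patch is worn, and an off-patch alarm lengthens that time. A correlation between wristband AF and patch AF over the whole 4 months therefore partly measures the extra ECG time that the alarm itself brought about.

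**Working it through.** **1. The plan's own figures.** Inputs from Protocol Section 7 and SAP Section 7: 1,000 per arm, 5% versus 0.5%, two-sided alpha 0.05, stated power above 0.99. With the pooled normal approximation,

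power = Φ{ [ |p1 − p2| − 1.96·√(2·p̄(1 − p̄)/n) ] / √( [p1(1 − p1) + p2(1 − p2)]/n ) }

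= Φ{ (0.045 − 1.96 × 0.00731) / 0.00724 } = Φ(4.23), above 0.99.

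Exact enumeration of Fisher's test agrees. The minimal sizes of 320 and 430 per arm also reproduce (319 and 429 with continuity correction), as does the SAP's 98% for 2% versus 0.1% (98.7%).

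**2. Does triggered-patch AF count, and where?** By inference, yes. Both definitions accept any qualifying patch AF, and nothing excludes a triggered patch. Delayed-arm devices are sent 4 months after consent, and SAP Section 4 ends that arm's comparison at 4 months, so such cases can arise only in the immediate arm. SAP Section 7 states the later-of rule for both arms together; I take the arm-specific rule in Section 4 as governing.

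**3. Possible size.** The documents give neither the number of wearers in the immediate arm (250 would be half of about 500) nor the yield of triggered patches. Both are assumed here. Extra cases = wearers × extra yield, set against 5% × 1,000 = 50 expected cases. The scheduled-only rate holds the total at 5%, and power is against 0.5%.

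| Wearers | Extra yield | Extra cases | Percentage points | Share of 50 | Scheduled-only rate | Power |
|---|---|---|---|---|---|---|
| 125 | 1% | 1.25 | 0.125 | 2.5% | 4.875% | >0.99 |
| 125 | 5% | 6.25 | 0.625 | 12.5% | 4.375% | >0.99 |
| 250 | 1% | 2.5 | 0.25 | 5% | 4.75% | >0.99 |
| 250 | 2% | 5 | 0.5 | 10% | 4.5% | >0.99 |
| 250 | 5% | 12.5 | 1.25 | 25% | 3.75% | >0.99 |
| 500 | 5% | 25 | 2.5 | 50% | 2.5% | 0.96 |

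The last row is an upper bound with every wearer in the immediate arm. Its power is Φ{ (0.020 − 1.96 × 0.00544) / 0.00542 } = Φ(1.72) = 0.96, and exact Fisher also gives 0.96.

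**4. ECG time.** Scheduled: 2 × 14 = 28 days. With one triggered patch: 28 + 14 = 42 days, or 50% more.

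**5. Direction of the effect on the device comparison.** Suppose the wristband carries no information, each 14-day patch shows AF with probability 2.5% (assumed), and patches are independent (assumed). Then P(any patch positive) = 1 − (1 − 0.025)^k:

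- k = 2, no triggered patch: 1 − 0.975² = 4.9%
- k = 3, one triggered patch: 1 − 0.975³ = 7.3%

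The ratio is about 1.5 although the wristband is uninformative. It falls toward 1 as results within a person become strongly correlated. Restricting to overlapping wear does not fully remove the problem, because the triggered window is itself concurrent wear and exists only for people whom the wristband flagged.

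**The case against.** The Protocol does not define its strategy as two patches only. Its Background proposes to study two monitoring methods, and it describes the confirmatory patch openly. The primary endpoint compares the monitored with the delayed cohort, includes claims diagnoses, and is nowhere called a two-patch yield. The SAP Section 7 phrase that describes the exposure as Zio patch monitoring belongs to the matched 12-month study. All of this stands: the issue is what the yield describes.

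A reader might infer that the primary result is biased or its yield falsely inflated. The documents do not support that. Triggered AF must be seen on ECG for at least 30 seconds and adjudicated, and analysis is by randomised arm, so self-selection into the sub-study does not break the comparison.

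A reader might also infer that agreement between the devices is built in. That is too strong. A triggered patch can refute the alarm, the alarm itself occurs off-patch, and SAP Section 5 limits true and false positives to overlapping wear. What survives is enrichment in an analysis labelled exploratory.

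The window point is narrow. *Final patch* most naturally means the second scheduled one, and only a late alarm could extend follow-up.

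Finally, making scheduled-only AF the primary yield would discard real cases from an intention-to-treat endpoint. Participants, and providers where permitted, are told of new diagnoses, so some of those cases would return through claims. This objection is sound and shapes the fix.

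**Conclusion.** The point holds as a matter of separation and description. As written, AF first found on a wristband-triggered patch counts toward the primary endpoint in the immediate arm only, and no planned analysis shows how much of the yield it contributes. The randomised test remains valid, and power stays at 0.96 or higher across the assumed range. The contribution cannot be estimated from the documents: 125 to 500 wearers and 1% to 5% extra yield give about 0.1 to 2.5 percentage points on an expected 5%, from trivial to material.

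In the device comparison, the SAP Section 3 correlation has no overlap limit and uses ECG time that only wristband-positive people receive (42 against 28 days with one triggered patch). The direction is toward association. The ratio of about 1.5 illustrates that direction under independence and is not an estimate for this trial.

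**What to change.** Change the SAP wording only; no change to the confirmatory patch is proposed.

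- State that triggered-patch AF counts, and keep the all-patch intention-to-treat endpoint as primary.
- Use the recorded serial numbers, dates and sub-study flag to tag each patch as scheduled or triggered.
- Prespecify a sensitivity analysis that counts AF from scheduled patches, or from claims not preceded by a triggered-patch diagnosis. Report AF first seen on a triggered patch as a separate line.
- In SAP Sections 4 and 7, define the final patch as the second scheduled one.
- Limit the wristband-versus-patch analysis to scheduled overlapping wear, reconcile SAP Section 3 with Section 5, and report the confirmation rate of triggered patches separately.

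**Cost.** A little more analysis work on data already held, and a scheduled-patch yield that may be lower than the headline. The sensitivity analysis may undercount if people diagnosed on a triggered patch skip their second scheduled one, so it should be read beside the primary result.
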